We will recruit a cohort of patients with minor stroke (NIHSS <8, modified Rankin score 0-2). Following baseline assessment of depression, fatigue, cognition, functional status, and patient satisfaction, individuals will be randomized to a standard 8 week MBSR course aimed at improving attention and concentration, and reducing anxiety and depression, or a bi-monthly standard Stroke Support Group (SSG). All patients will undergo reassessment post-intervention (~4-6 months post-infarct), along with MEG pre- and post-intervention. Participants will undergo neuroimaging pre- and post-intervention. We will evaluate differences in activation patterns and functional connectivity both at rest and during a visual cognitive task. We hypothesize that both groups will initially exhibit abnormal frontal lobe function compared to controls; however, after MBSR this will improve versus the SSG group.

Participants will also be administered a pre- and post-intervention Montreal Cognitive Assessment (MoCA), along with a battery of cognitive tasks to measure attention, concentration, processing speed, and executive function. Performance will be compared pre- and post-intervention, and for MBSR versus SSG participants. We hypothesize scores will be significantly better following MBSR compared to the SSG group. Finally, the PHQ9 and other measures of patient-reported outcomes (eg., mood) will be given to patients pre- and post-intervention and compared across groups at each time point. We hypothesize MBSR will improve rates of depression/anxiety compared to SSG. We will also evaluate patient satisfaction scores, measures of functional recovery: the modified Rankin scale (mRS) and Barthel Index (BI), and the likelihood of successful return to work. Individuals with minor stroke have tremendous potential to return to their baseline level of function, though often struggle. If effective in reducing post stroke mood and cognitive disorders for those with minor stroke, allowing them to return to work, MBSR will significantly reduce post-stroke morbidity and improve quality of life.

---

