#### 4. Study Procedures

- a. This is a prospective, randomized, controlled, longitudinal clinical trial that will make use of the following protocol:
  - Patients are admitted to the hospital for acute stroke and undergo work-up including MRI; they are entered into our Clinical Outcomes Database (routine clinical care, database is HIPAA compliant and has prior IRB approval). At this point, or at their first follow-up clinic visit, they will be identified and approached about participation in the study.
  - All patients are scheduled for an appointment in the Bayview Stroke Intervention Clinic (BaSIC) approximately 4-6 weeks +/- 4 weeks post-stroke
  - Seen at 4-6 weeks (routine care)- consented and tested if enrolled (per research protocol, as part of a prior approved study on Stroke Recovery)
  - Those meeting inclusion criteria for the Mindfulness and MEG study will be consented, randomized, and undergo the following additional procedures:
    - 1 month MEG visit at the University of Maryland (UMD, our current partner for our ongoing MEG study)- brain activity will be measured at rest and during cognitive tasks
    - EITHER 8 weeks of either MBSR Training and guided meditation using provided resources or participation in our bi-monthly Stroke Support Group
    - Repeat MEG following intervention (approximately 4-6 months post-stroke)
      - UMD MEG Protocol:
        - Magnetic fields will be recorded using a 275-channel whole-head MEG system (KIT System)

The MEG System non- invasively measures the magnetoencephalographic (MEG) signals produced by electrically active tissue of the brain. These signals are recorded by a computerized data acquisition system, displayed, and may then be interpreted by trained physicians to help localize these active areas. The location may then be correlated with anatomical information of the brain. MEG is routinely used to identify the locations of visual, auditory, somatosensory, and motor cortex in the brain. \* MEG is also used to non-invasively locate regions of epileptic activity within the brain. The localization information provided by MEG may be used, in conjunction with other diagnostic data, in neurosurgical planning.

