#### *Indications used in this study*

The MEG System will non-invasively measure the MEG signals produced by electrically active tissue of the brain. These signals will be recorded by a computerized data acquisition system, displayed, and then be interpreted by trained *scientists* to help *characterize* and to localize these active areas *while the subjects are resting but awake, and while they perform several cognitive tasks*. The location will then be correlated with anatomical information of a *standard brain model or the subject's head MRI*. MEG will be used to identify the locations of visual, auditory, somatosensory, and motor cortex in the brain.

- The total length of the MEG recordings will depend on the length of the tasks (an estimate of 60 min has been used).
- Finally, patients will return for their 2nd post-stroke follow-up in BaSIC (routine care) and testing (if part of the Mindfulness or Recovery Study) following intervention (approximately 4-6 months post-stroke)
- b. We currently follow patients with minor stroke for 12 months post-infarct. They undergo additional testing as part of the study at their 1, 6, and 12 month follow-up visits. For this study, we will use MEG to map brain activity in individuals at the 1 and 6 month follow-up time points. This will require 2 visits to clinic at which time they will undergo testing, intervention with MBSR versus a Stroke Support Group, and 2 trips to the University of Maryland for MEG.
- c. The study is not formally blinded, as all patients who undergo imaging and intervention will have a stroke. However, the team at UMD will be initially blinded to stroke location, clinical symptoms, and

intervention. A control population for comparison already exists and for this pilot study we are interested in imaging affected individuals to determine differences.

- d. All participants will receive routine care. Intervention with MBSR/Support Group, and MEG testing will be performed above and beyond typical care and does not otherwise alter the treatment or monitoring course.
- e. There is a control group of patients of similar age without stroke who have already undergone MEG imaging and will be used as non-stroke control group; though the Stroke Support Group will allow for adjustment for socialization and activity as confounding factors (as the alternative intervention to MBSR)

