**To determine the effect of MBSR on abnormal cerebral activation patterns on MEG after stroke:**

- Participants will undergo neuroimaging at 1 and 6 months post-stroke. Participants in the MBSR and SSG will be compared to a previously collected group of controls with no infarct. Source localized whole brain activation will be assessed to determine overall differences in space and time between each group (MBSR v SSG) versus controls for each time point. Cluster-based permutation tests (based on independent measures t values) will then be performed to evaluate mean differences in activation for ROIs between groups at each time point. Paired t values will allow for evaluation of changes over time within each group. Amplitude of peak activation and spike latency will be assessed. ANCOVA will allow for adjustment of potential confounders.
- *Sample Size.* We have been able to demonstrate results at or approaching statistical significance for our current cohort of patients with minor stroke versus controls after enrolling only 9 participants. This number is similar to many other published studies evaluating differences in activation patterns on MEG. We do anticipate less of a difference when comparing stroke patients to other stroke patients, and will therefore increase our sample size to at least 20 individuals in each group. There remains a chance given the potential for improvement in both groups, that we may still be inadequately powered to detect long-term outcomes in this pilot study; however results will also allow treatment effect estimates that will inform a larger clinical trial.

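### At the pre-intervention MEG, testing each arm separately against one shared control group loses precision and gives two correlated tests of one question; one pooled test would do better

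*Combined protocol and SAP*

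**What the plan says.** Section 7 sets MEG scans at 1 and 6 months and names the comparison group: "Participants in the MBSR and SSG will be compared to a previously collected group of controls with no infarct". The next sentence gives the form of the comparison: "overall differences in space and time between each group (MBSR v SSG) versus controls for each time point". The tests follow: "Cluster-based permutation tests (based on independent measures t values) will then be performed to evaluate mean differences in activation for ROIs", again between groups at each time point.

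The Abstract states what is expected at the first scan: "We hypothesize that both groups will initially exhibit abnormal frontal lobe function compared to controls". Section 4 puts allocation ahead of the study procedures, the first of which is the 1-month MEG: "Those meeting inclusion criteria for the Mindfulness and MEG study will be consented, randomized, and undergo the following additional procedures". The intervention comes after that scan.

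The controls are a single existing group, described in Section 4, item e: "There is a control group of patients of similar age without stroke who have already undergone MEG imaging". Their number is not given. On arm size, the investigators "will therefore increase our sample size to at least 20 individuals in each group".

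Objective 1 in Section 2 also compares the two arms with each other, with group differences examined at each time point. No section plans a pooled stroke-versus-control test at 1 month, allows for the shared controls, or adjusts for the two tests.

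**The concern.** At the 1-month scan the arm labels carry no information about brain activity. Participants have been randomised but not treated, so the arms differ only by chance. Whether minor-stroke patients are abnormal relative to people without infarct is therefore one question, and all randomised participants bear on it. Splitting them uses half the stroke sample in each test.

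The two tests also share their controls. If the control mean happens to lie high or low, both arm-versus-control differences move the same way, so the results are correlated.

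Two things are at stake. The first is precision in a comparison that supplies the premise of Objective 1, in a trial whose own sample-size paragraph concedes possible inadequate power. The second is interpretation. Two tests of one question can disagree by chance, and the plan does not say how to read a result that is significant in one arm and not in the other.

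**Working it through.** **The plan's own figure.** Section 7 gives at least 20 per arm, with no alpha, power, effect size or SD, so there is no calculation to reproduce. The stated support is an earlier result "at or approaching statistical significance for our current cohort of patients with minor stroke versus controls after enrolling only 9 participants". For scale, 20 against 20 has 80% power at a difference of 0.91 SD (two-sided 5% t-test).

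**Inputs**
- n = 20 per arm (Section 7), so 40 pooled. Equal allocation is assumed.
- m = number of controls. Not stated; 9, 20 and 30 are assumed to show a range.
- Two-sided alpha of 0.05. Not stated; assumed.
- True stroke-versus-control difference d = 0.8 SD where one is needed. Not stated; assumed.
- A single t-test on one measure, standing in for the cluster-based procedure.

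**Step 1: standard error, in SD units.** SE = √(1/n + 1/m). For m = 20, one arm gives √(1/20 + 1/20) = 0.316 and the pooled sample gives √(1/40 + 1/20) = 0.274. The reduction is 1 − 0.274/0.316 = 13%.

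**Step 2: difference detectable with 80% power.** Noncentral t with n + m − 2 degrees of freedom and noncentrality d/SE. As a check for m = 20, the normal approximation (1.96 + 0.84) × SE gives 2.80 × 0.316 = 0.88 and 2.80 × 0.274 = 0.77. These are slightly below the exact 0.91 and 0.78, as expected.

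**Step 3: correlation of the two arm-versus-control statistics.** ρ = (1/m)/(1/20 + 1/m) = 20/(20 + m).

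**Step 4: joint behaviour of the two split tests.** 400,000 simulated trials for each m and d, with two arms of 20 sharing m controls.

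| | m = 9 | m = 20 | m = 30 |
|---|---|---|---|
| SE, one arm | 0.401 | 0.316 | 0.289 |
| SE, pooled | 0.369 | 0.274 | 0.242 |
| Reduction in SE | 8% | 13% | 16% |
| Detectable difference, one arm (SD) | 1.17 | 0.91 | 0.83 |
| Detectable difference, pooled (SD) | 1.06 | 0.78 | 0.69 |
| Power at d = 0.8, one arm | 48% | 69% | 78% |
| Power at d = 0.8, pooled | 57% | 82% | 90% |
| ρ between the split tests | 0.69 | 0.50 | 0.40 |
| d = 0.8: exactly one arm significant | 27% | 29% | 27% |
| d = 0: at least one arm significant | 8.5% | 9.0% | 9.3% |
| d = 0: both arms significant | 1.5% | 0.9% | 0.7% |

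With no true difference, one pooled test is significant in 5% of trials.

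**Step 5: a like-for-like check on requiring both arms.** At d = 0.8 both split tests are significant in 35%, 55% and 64% of trials. That rule has the false-positive rate in the last row of the table. Running the pooled test at the same rate gives power of about 37%, 59% and 70%. The gain at equal error is therefore roughly 2 to 6 percentage points.

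**The case against.** **The wording may already mean pooling.** The sentence introducing the controls can be read that way. The sentence after it specifies each group, and the Abstract speaks of both groups, so the separate reading is the natural one. If pooling was intended, the text still needs to say so.

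**A large power loss.** A reader might set 35%, 55% and 64% (both arms significant) against 57%, 82% and 90% (one pooled test) and infer a loss of more than 20 points. That comparison mixes error rates, as Step 5 shows. Nor does the plan say that both tests must be significant; the Abstract states an expectation. The fair comparison is one split test against one pooled test.

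**Two false confirmations.** A reader might also infer that one chance deviation in the controls will pass for two independent findings. The documents never describe the comparisons as independent or as confirming each other. A false result in both arms (0.7% to 1.5%) is also rarer than a false pooled result (5%). What stands is that the tests are correlated, and that accepting either arm as evidence carries about a 9% false-positive rate.

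**Reuse of the pilot controls.** The controls may be those behind the earlier 9-participant result. The documents do not say so and give no pilot test statistic, so no false-confirmation rate can be attached. Pooling would not address that matter in any case.

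**Baseline imbalance is already examined.** Objective 1 compares the arms directly at each time point. This stands: a direct comparison is the right way to ask whether the arms started apart, and it limits the harm from a split result. It also leaves the separate arm-versus-control tests with less to contribute at 1 month.

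**Low consequence.** This is a pilot, the comparison is not the treatment contrast, and the real test is cluster-based. All of this stands and sets the priority.

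**Conclusion.** The point holds in a limited form. Before treatment, testing the arms separately against one control group is less precise than a pooled test and yields two correlated answers to one question. Pooling lowers the standard error by 8% to 16% and the detectable difference by 0.11 to 0.14 SD across 9 to 30 controls. It also removes the chance, a little over one in four at a true difference of 0.8 SD, that the arms disagree on significance although they come from the same population.

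These sizes rest on the assumed control numbers, alpha and effect size, and on single t-tests. The direction of each effect does not depend on those choices, but the absolute percentages will not carry over to cluster-based permutation tests. With very few controls the gain is modest, because no number of stroke participants can bring the standard error below √(1/m), which is 0.333 SD for 9 controls. Pooling also does not remove chance error in the controls.

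The point is confined to the 1-month stroke-versus-control comparison. After the intervention the arms may truly differ, so separate comparisons are reasonable there. Priority is low to moderate: the comparison supports Objective 1 but does not estimate the effect of MBSR.

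**What to change.** In Section 7, specify that the stroke-versus-control comparison at 1 month is one test of all randomised participants with a pre-intervention scan (about 40) against the controls. Report arm-specific results at that scan descriptively, without separate tests against controls. State the number of controls. Align the Abstract's hypothesis so that it refers to stroke participants as a whole at the first scan.

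Keep the arms separate for the post-intervention analyses, including MBSR versus SSG.

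The cost is wording only. No participant, scan or assessment is added, and the number of tests falls by one for each MEG measure compared at 1 month.

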## 2. Objectives

Objective 1: To determine the effect of MBSR on abnormal cerebral activation patterns on MEG after stroke. Participants will undergo neuroimaging pre- and post-intervention. We will evaluate differences in activation patterns both at rest and during a visual cognitive task using cluster-based permutation tests. Patients in the MBSR and SSG groups will be compared to one another and to patients with no infarct

(previously collected cohort). T-tests and ANCOVA will be used to determine differences between groups at each time point. Functional connectivity studies will also be performed to evaluate differences between groups.

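### MEG regions of interest are tested after a whole-brain comparison, with no region, source or multiplicity correction stated, although the hypothesis is about the frontal lobes

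*Combined protocol and SAP*

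**What the plan says.** The MEG analysis is in section 7 (Study Statistics), under the heading on the effect of MBSR on cerebral activation. It has two steps in a stated order.

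- Step 1: "Source localized whole brain activation will be assessed to determine overall differences in space and time between each group (MBSR v SSG) versus controls", at each time point.
- Step 2: cluster-based permutation tests, built on independent-samples t values, "will then be performed to evaluate mean differences in activation for ROIs between groups at each time point".

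Step 2 is the only place in the document where ROIs appear. There is no list, number, atlas, hold-out sample or correction across ROIs. Section 2 (Objective 1) names the same kind of test more generally, without ROIs: "We will evaluate differences in activation patterns both at rest and during a visual cognitive task using cluster-based permutation tests". It also says that the MBSR and SSG groups are compared both with each other and with the non-infarct cohort.

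The hypothesis in section 1 (Abstract) is regional: "both groups will initially exhibit abnormal frontal lobe function compared to controls; however, after MBSR this will improve versus the SSG group". Sections 1 and 3 report abnormal resting frontal activity in earlier MEG work. Yet neither the MEG outcomes in section 7a nor the MEG analysis names a frontal region.

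**The concern.** Two gaps follow from this.

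The first is where the ROIs come from. If the map from step 1 guides which regions enter step 2, the same recordings select and test the region, and the nominal level of the step 2 test need not hold. Effect estimates suffer too. Section 7 expects this pilot to supply treatment effect estimates for a larger trial, and a difference read off in a region chosen because its difference was large is biased upward.

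The second is what a significant result would mean. A cluster-based permutation test run over the whole brain rejects the null of no difference anywhere in the space searched. Its p-value does not certify where the cluster lies or how far it extends. The question asked is about the frontal lobes, so a whole-brain cluster that touches frontal cortex would not by itself answer it.

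**Working it through.** **Inputs from the plan.** At least 20 per group (section 7), and a previously collected control group of unstated size. The 20 comes with no alpha, power, effect size or SD, so there is no calculation to reproduce. It is used here only as an input.

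**Assumptions.** Two-sided 5%, equal arms, 10 or 20 controls, K candidate regions with equal between-region correlation, no true difference anywhere, one time point. The single region with the largest absolute t in the selecting contrast is carried forward and tested without correction.

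**Why the route matters.** Let M, S and C be the mean values for MBSR, SSG and controls in one region, with equal variance.

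- *Same contrast selects and tests.* With independent regions the error is 1 − 0.95^K: 23% for K = 5, 40% for 10, 64% for 20 and 97% for 68.
- *Selected on M − C (or S − C), tested on M − S.* The two contrasts share one arm. Their correlation in absolute size is (1/20) / √[(2/20)(1/20 + 1/n_C)]. With 20 controls this is 0.05/√(0.10 × 0.10) = 0.50. With 10 controls it is 0.05/√(0.10 × 0.15) = 0.41. The inflation is therefore partial.
- *Selected on pooled stroke v controls, tested on M − S.* With equal arms the covariance of (M + S)/2 − C with M − S is [Var(M) − Var(S)]/2 = 0. No inflation is expected.

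**Simulation.** 4,000 null runs per setting, correlation 0 or 0.5, 10 or 20 controls; ranges are over these settings.

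| Candidate regions | Fixed in advance | Chosen on pooled stroke v controls, tested MBSR v SSG | Chosen on larger group-v-control difference, tested MBSR v SSG | Same contrast selects and tests |
|---|---|---|---|---|
| 10 | 4.6–5.0% | 4.7–5.3% | 13.0–17.1% | 29.0–40.5% |
| 20 | 4.6–5.4% | 4.9–5.4% | 15.5–20.4% | 42.5–64.5% |
| 68 | 4.6–5.3% | 4.5–4.8% | 18.4–28.4% | 69.9–97.0% |

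Widening to 5–68 regions and correlation 0–0.6 gives about 5%, about 5%, about 10–29% and about 16–97% for the four routes.

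**Effect estimates.** With no true effect and the same contrast selecting and estimating, the mean absolute standardized difference is 0.54–0.61 in the best of 10 regions and 0.71–0.87 in the best of 68. It is about 0.26 in a fixed region.

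**Location.** In a one-dimensional toy model (20 v 20) the true effect lay wholly outside, but bordering, a zone labelled frontal. When the signal had no spread, about 5% of significant results had a significant cluster reaching into that zone. When the signal was blurred like the noise, as an assumed stand-in for source leakage, 26–41% did. This shows the direction of the problem and is not an estimate for this trial.

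**The case against.** A reader might infer that the ROI p-values are circular. The documents do not support that. The text gives an order of analyses and never says that ROIs are drawn from the whole-brain map. Step 1 is also each stroke group against controls, not MBSR against SSG, so the highest rates do not describe the documented step 1 followed by the key randomized comparison. They apply only if one contrast is used twice without correction. Objective 1 leaves room for that in the comparisons with controls. This part of the objection stands and sets the size of the point.

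A reader might also infer that a cluster test can never establish a frontal effect. That is too broad. Step 2 concerns ROI means, and a test confined to a frontal ROI fixed in advance can support an effect there, subject to leakage. Nor does the plan say that cluster extent will be used as proof of location.

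Cluster permutation tests also correct over the space they search. A maximum-statistic permutation over all 10 or all 68 regions held 5–6% in a check of 500 runs. This is right, but it helps only if the test covers every candidate region, and then the p-value again refers to a difference somewhere. If the test is confined to a region chosen beforehand, the source of that region decides whether the level holds.

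Finally, earlier work already points to the frontal lobes, the MEG team is initially blinded to intervention (section 4c), and this is a pilot. These points soften the concern without closing it. The frontal target never reaches the outcomes or the analysis. Blinding is only initial, and it would not stop a choice based on coded groups or on stroke v controls.

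**Conclusion.** The point holds as an unspecified ROI source, with no correction across ROIs, in a plan whose hypothesis is regional. Circular testing is possible under the wording but not shown. The false-positive rate stays at about 5% if ROIs are fixed in advance or, with equal arms, chosen on pooled stroke v controls. It rises to about 10–29% on the route closest to the stated step 1, and to about 16–97% if one contrast both selects and tests. The number of regions, their correlation, the number of controls, the alpha level and the absence of correction are assumptions, so these rates are illustrations and not trial figures. Separately, a significant whole-brain cluster would leave the frontal hypothesis unproven. This should be settled before post-intervention MEG data are opened; it does not invalidate the design.

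**What to change.** Before post-intervention data are opened, state the following in section 7.

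- Name one frontal ROI from an anatomical atlas. If it is taken from the earlier MEG cohort instead, use it only for MBSR v SSG. The existing controls appear to belong to that earlier work, so the ROI would not be independent for comparisons with them. In a simulation that chose the ROI from 9 earlier patients v those controls, testing a new arm against the same controls gave 8–26% false positives, while MBSR v SSG stayed at about 5%.
- Average the resting measure over the ROI to give one number per participant per scan.
- Compare MBSR with SSG on the post-intervention value by ANCOVA, with the pre-intervention value as covariate. The plan already names ANCOVA, but for confounders.
- If more ROIs are kept, list them and correct across them.
- Label whole-brain cluster tests exploratory. Do not use them to choose ROIs or to claim location.

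The cost is SAP wording, with no new data or participants. The downside is that effects outside the chosen region become exploratory.
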